## ABBREVIATIONS

Abbreviation	Definition
AE	Adverse event
ALP	Alkaline phosphatase
ALT	Alanine aminotransferase
AST	Aspartate aminotransferase
ATC	Anatomical Therapeutic Chemical
BMI	Body mass index
BUN	Blood urine nitrogen
CGI-c	Clinical Global Impression - change
CGRP	Calcitonin gene-related peptide
CI	Confidence interval
CK	Creatine kinase
COVID-19	Coronavirus Disease 2019
CRF	Case report form
CSR	Clinical study report
CTMS	Clinical trial management system
CYP3A4	Cytochrome P450 3A4
ECG	Electrocardiogram
eDiary	Electronic diary
eDISH	Evaluation of drug-induced serious hepatotoxicity
eGFR	Estimated glomerular filtration rate
EOS	End of study
EOT	End of treatment
HDL	High-density lipoprotein
IP	Investigational product
IWRS	Interactive web response system
LDL	Low-density lipoprotein
LFT	Liver function test
LT	Long-term treatment
MDRD	Modification of Diet in Renal Disease
MIDAS	Migraine Disability Assessment
MSQ	Migraine Specific Quality of Life Questionnaire
OP	Observation phase
PID	Patient identifier

---

Abbreviation	Definition
PoM	Preference of medication
PT	Preferred term
S-STS	Sheehan-Suicidality Tracking Scale
SAE	Serious adverse event
SAP	Statistical analysis plan
SOC	System organ class
SM	Satisfaction with Medication
TEAE	Treatment-emergent adverse event
TBL	Total bilirubin
TLF	Table listing figure
ULN	Upper limit of normal

---

## 1 BACKGROUND AND RATIONALE

This document presents the statistical analysis plan (SAP) for Biohaven Pharmaceuticals, Protocol BHV3500-202: A Phase 2/3 Open-label, Long-Term, Safety Trial of BHV3500 (zavegeptan) Intranasal (IN) for the Acute Treatment of Migraine.

This SAP contains the analysis details and methodology to answer the study objectives, including planned tables, listings, and figures (TLFs), which provide the basis for the results section of the clinical study report (CSR).

### 1.1 Research Hypothesis

Zavegeptan is safe and well tolerated in the treatment of migraine.

### 1.2 Schedule of Analyses

During the course of this study, safety and exposure data are monitored on an ongoing basis. Interim analyses may be conducted after an interim database lock that is prior to last patient last visit. The CSR is produced after the last patient last visit and final database lock. All analyses described in this SAP are performed after the final database lock.

[figure not shown]
## 2 STUDY DESCRIPTION

### 2.1 Study Design

This is a multi-center, open-label study to assess the safety and tolerability of long-term use of IN zavegeptan, taken up to 8 times per month (every 28 days) in subjects with migraine. The study drug, zavegeptan (BHV-3500), is formulated as a 10 mg IN dose and is administered using an Aptar Unit Dose System (UDS) liquid spray device. Each UDS device contains a single dose of study drug zavegeptan. The subjects are instructed to take their study drug, when they have a migraine headache, up to 8 times per month.

The design of the study is shown in [Figure 1](#). The study screens approximately 800 subjects to treat approximately 600 subjects. After completion of screening procedures and a 28-day observation phase (OP), eligible subjects may participate in the study up to 52 weeks in the long-term treatment (LTT) phase. Study visits are roughly every 2 weeks during the first month and then every 4 weeks until Week 52 in the LTT phase. Subjects who complete or discontinue early from LTT phase also complete a follow-up visit approximately 14 days after the End of Treatment (EOT) visit.

**Figure 1: Study Schematic**

## 2.2 Treatment Assignment

The Interactive Web Response System (IWRS) assigns a subject identifier number at the screening visit.

If the subject is deemed eligible to participate in the study at the baseline visit, then the IWRS assigns specific container numbers for all open-label study drug to be dispensed at the baseline visit and subsequent visits in the LTT phase.

## 2.3 Blinding and Unblinding

This is an open-label study. All TLFs produced before or after data base lock are produced with the actual treatment group.

## 2.4 Protocol and Protocol Amendments

BHV3500-202 SAP Versions 1.0, 2.0, 3.0, 4.0, 5.0, and 6.0 are based on BHV3500-202 Protocol Version 2.0.

# 3 STUDY OBJECTIVES AND ESTIMANDS

## 3.1 Objectives

### 3.1.1 Primary Objective

To evaluate the safety and tolerability of zavegepant.

### **3.1.2 Secondary Objectives**

Not applicable.

### **3.1.3 Exploratory Objectives**

1. To evaluate the frequency of adverse events (AEs) potentially associated with drug abuse.
2. To evaluate frequency of AEs indicating medication-overuse headache.
3. To evaluate the frequency and intensity of hepatic-related AEs.
4. To evaluate the frequency of liver function test (LFT) elevations (alanine aminotransferase [ALT], aspartate aminotransferase [AST], alkaline phosphatase [ALP], and total bilirubin [TBL]) based on fold changes above the upper limit of normal (ULN).
5. To evaluate the frequency of ALT or AST  $> 3x$  ULN concurrent with TBL  $> 2x$  ULN.
6. To evaluate the frequency of ALT or AST  $> 3x$  ULN in temporal association with nausea, vomiting, anorexia, abdominal pain, or fatigue.
7. To evaluate Sheehan-Suicidality Tracking Scale (S-STS) scores and changes from baseline.
8. To evaluate the frequency of nasal edema and inflammation from nasal inspection.
9. To evaluate the reduction from the OP in the number of migraine days per month by intensity.
10. To evaluate Migraine-Specific Quality of Life Questionnaire v 2.1 (MSQ) domain scores and changes from baseline.
11. To evaluate Preference of Medication (PoM).
12. To evaluate Satisfaction with Medication (SM).
13. To evaluate Migraine Disability Assessment (MIDAS) scores and changes from baseline.
14. To evaluate Clinical Global Impression - change (CGI-c).

## **3.2 Estimands**

An estimand is the target of estimation to address the scientific question of interest posed by a study objective. The 4 attributes of an estimand include the population of interest, endpoint of interest, summary of the endpoint, and specification of how intercurrent events are reflected in the scientific question of interest.

For all objectives, the population of interest is defined through appropriate inclusion/exclusion criteria to reflect the targeted patient population for approval. Refer to the protocol for inclusion/exclusion criteria.

## Intercurrent Events

Intercurrent events are those that occur after treatment initiation and either preclude observation of the endpoint or affect its interpretation. Study drug discontinuation before the time point of interest defining the endpoint is considered an intercurrent event.

- For safety objectives, study drug discontinuation is handled with a “while-on-treatment strategy,” i.e., response to treatment prior to the occurrence of the intercurrent event of interest, such that all observed values of the endpoint of interest are used prior to study drug discontinuation.
- For outcomes research and other objectives, study drug discontinuation is handled with a “treatment policy strategy”, i.e., the occurrence of the intercurrent event is considered irrelevant, such that all observed values of the endpoint of interest are used regardless of study drug discontinuation.

Refer to Section 4.1 for analysis sets that are used to assess endpoints.

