⁴ Full physical exam at screening and EoT; targeted physical exam guided by signs and symptoms at all other specified visits.

⁵ If the end of treatment physical exam from BHV3500-301 was done within 4 weeks of the screening visit for BHV3500-202, it does not need to be completed at screening. The data from the BHV3500-301 physical exam must be entered in the BHV3500-202 CRF.

⁶ Height collected at screening only.

⁷ Hematology includes hemoglobin, hematocrit, RBCs, WBCs with differential, platelets; Chemistry includes creatine kinase, sodium, potassium, chloride, bicarbonate, calcium; glucose, HbA1c, BUN (urea), serum creatinine, uric acid, LDH, total protein, albumin.

⁸ LFTs includes AST, ALT, Alkaline Phosphatase, and bilirubin (total, direct, indirect)

⁹ Lipid panel includes cholesterol, LDL, HDL, and triglycerides

¹⁰ The BHV3500-301 EoT ECG can be used as the screening ECG for BHV3500-202 if the visits are done on same day.

¹¹ Urinalysis includes pH, specific gravity, ketones, nitrites, urobilinogen, leukocyte esterase, protein, glucose, and blood. If blood, protein or leukocytes are positive, reflex to microscopic examination

Week 2 Follow-up Safety Visit (14 days after EOT visit +/- 2 days) ¹		X (urine) ^{Error!} Bookmark not defined.	×	×				
Weeks 8, 12, 16, 20, 24, 28, 32, 36, 40, 44, 48, 52 (or EoT) (all visits +/- 7 days) ¹		X (urine) ¹³	X	X ¹⁵	X	X (Weeks 12, 24, 36, 52/EoT only)	X (Week 52/EoT)	X (Week 52/EoT)
$\frac{\text{Week}}{4 \text{ (Day}}$ $\frac{29 + -}{2 \text{ days})^{1}}$		X (urine)	×	X	X			
$\frac{\text{Week 2}}{\text{(Day)}}$ $\frac{15}{+/-2 \text{ days)}^{1}}$			×	×	X			
Baseline Visit (Day 1)			×		X			
Visit Up to 5 days prior to Baseline Visit		X (serum)	×	X	X	×		
Observation Phase (28 days +/- 2 days)					X			
Screening Visit	X	X (urine)	×	X				
Procedure	FSH, if applicable, to determine WOCBP status ¹²	Pregnancy Test	AE and SAE assessment ¹⁴	Sheehan Suicidality Tracking Scale	Subject report of migraine occurrence and intensity	Migraine-Specific Quality of Life Questionnaire (MSQ) v 2.1	Preference of Medication	Satisfaction with Medication

¹² If WOCBP status was determined by FSH in BHV3500-301 the subject is considered to have the same status in BHV3500-202

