6.6 Early Discontinuation from the Study

Subjects must discontinue investigational product for any of the following reasons:

- Withdrawal of informed consent (subject's decision to withdraw for any reason)
- Any clinical AE, laboratory abnormality or intercurrent illness which, in the opinion of the
 investigator or sponsor, indicates that continued participation in the study is not in the best
 interest of the subject
- Pregnancy
- No migraine treated with study drug prior to the week 8 visit of the long-term treatment phase of the study
- Lack of efficacy of study medication

- Poor compliance with study procedures, including poor compliance with study medication dosing instructions.
- Infrequent study drug usage (defined as an average of <2 doses per month over 3 consecutive months).
- Please see Section 6.3.5 for guidance on study discontinuation based on results from the S-STS.
- eGFR \leq 40 (ml/min/1.73m²) using the estimated MDRD formula
- Termination of the study by Biohaven Pharmaceuticals
- Loss of ability to freely provide consent through imprisonment or involuntary incarceration for treatment of either a psychiatric or physical (e.g., infectious disease) illness

All subjects who discontinue should comply with protocol specified End of Treatment procedures as outlined in Table 1. The only exception to this requirement is when a subject withdraws consent for all study procedures or loses the ability to consent freely (i.e., is imprisoned or involuntarily incarcerated for the treatment of either a psychiatric or physical illness).

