	For the ideation subscale, behavior subscale, and total scores: 
 
• Worst (highest) score on-treatment and follow-up
 
• Change from baseline to worst score on-treatment and follow-up
 
• Number and percentage of subjects in each of 5 worst change from baseline score categories (< -1, -1, no change, 1, > 1) on-treatment and follow-up
 

Safety Endpoint	
Summary	Summary statistics and frequency for the safety analysis set with S-STS data
Intercurrent Events	Study drug discontinuation: while-on-treatment strategy
Objective	Frequency of nasal edema and inflammation from nasal inspection
Safety Endpoint	Number and percentage of subjects with local irritation AEs
Summary	Frequency for the safety analysis set
Intercurrent Events	Study drug discontinuation: while-on-treatment strategy
Objective	Reduction from the OP in the number of migraine days per month by intensity
Safety Endpoint	Values and changes from OP in the number of migraine days per month during LTT (1) over time by month and (2) overall, by migraine intensity (total; moderate or severe)
Summary	Summary statistics for values and changes from OP over time for the migraine analysis set
Intercurrent Events	Study drug discontinuation: treatment policy strategy
Objective	MSQ domain scores and changes from baseline
Outcomes Research Endpoint	Values and changes from baseline in the MSQ score over time for each dimension
Summary	Summary statistics for values and changes from baseline over time for each dimension for the safety analysis set
Intercurrent Events	Study drug discontinuation: treatment policy strategy
Objective	PoM
Outcomes Research Endpoint	Number and percentage of subjects in each of 5 preference categories (much better to much worse) of study medication relative to previous migraine medications
Summary	Frequency for the safety analysis set with PoM data
Intercurrent Events	Study drug discontinuation: treatment policy strategy
Objective	SM
Outcomes Research Endpoint	Number and percentage of subjects in each of 7 satisfaction categories (completely satisfied to completely dissatisfied) of study medication
Summary	Frequency for the safety analysis set with SM data
Intercurrent Events	Study drug discontinuation: treatment policy strategy

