### **6.1.3 *Missing Data***

All analyses are based on observed data without using imputation.

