### **eDiary Zavegepant Sprays per Month Over Time**

eDiary zavegepant sprays per month over time are tabulated as a continuous variable at each month in the LTT analysis period for the safety analysis set. This analysis is based on absolute spray counts per month. Using the example above for exposure categories, the subject has 4, 3, 5, 6, and 0 sprays per month in Months 1 through 5, respectively, and 5 months in the LTT period as determined by calculating the ceiling([LTT end date – LTT start date + 1]/28).

This is also tabulated for the safety analysis set with  $\geq 51$  weeks in the LTT period.

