- Scatter plot of percent change from OP in the number of moderate or severe migraine days per month in the overall LTT the y-axis versus number of moderate or severe migraine days per month in the OP on the x-axis
- Longitudinal plot of mean change from OP in the number of total migraine days per month on the y-axis versus month on the x-axis
- Longitudinal plot of mean change from OP in the number of moderate or severe migraine days per month on the y-axis versus month on the x-axis.

Scatter plots display a horizontal reference line at 0. Longitudinal plots display error bars denoting 95% CIs.

In the percent change/reduction analyses, subjects must also have  $\geq 1$  migraine day (absolute not prorated) of appropriate migraine intensity during the OP to be included.

A by-subject listing presents migraine attacks and intensity over time for the enrolled analysis set, and displays COVID-19 visit impact code for visits impacted by COVID-19 (see Section 9.1.5.2).

Another by-subject listing presents the number of migraine days per month during the OP, overall LTT, and by month during the LTT for the safety analysis set.

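### Migraine-day and outcomes-research endpoints are labelled treatment policy, but by-month and by-visit results describe only subjects still in LTT, so a trend can reflect who remains

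*SAP*

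**What the plan says.** **Label.** SAP 3.2 (Intercurrent Events) treats drug discontinuation as irrelevant for outcomes research and other objectives, so that "all observed values of the endpoint of interest are used regardless of study drug discontinuation". Table 2 repeats "Study drug discontinuation: treatment policy strategy" for migraine days, MSQ, PoM, SM, MIDAS and CGI-c.

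**Collection.** Protocol 6.6: "All subjects who discontinue should comply with protocol specified End of Treatment procedures as outlined in Table 1". In Protocol Table 1 the last MSQ entry reads "X (Weeks 12, 24, 36, 52/EoT only"). MIDAS and CGI-c follow the same visits, PoM and SM are taken at Week 52/EoT, and the follow-up column is blank for all five and for the migraine report. Provisioned diary devices are handed back at EOT (Protocol 4.3.5).

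**Estimator.** SAP 6.1.3: "All analyses are based on observed data without using imputation". Under SAP 6.4.6.1 a subject counts in a month only with at least 14 diary days in it. The planned output includes by-month mean changes with 95% CIs and a "Longitudinal plot of mean change from OP in the number of total migraine days per month on the y-axis versus month".

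**Exit.** Among the reasons for which study drug must stop, Protocol 6.6 lists "Infrequent study drug usage (defined as an average of <2 doses per month over 3 consecutive months"), and separately lack of efficacy.

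**Fixed cohort.** For sprays per month SAP 6.2.6.1 adds: "This is also tabulated for the safety analysis set with" at least 51 weeks in LTT. SAP 6.4.6.2 does the same for treated migraine days. Nothing equivalent is planned for change in migraine days, MSQ or MIDAS.

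**The concern.** A treatment-policy value at Month 12 needs an outcome at Month 12 from a subject who stopped at Month 5. The schedule asks for none, and nothing is imputed. What the by-month tables estimate is the mean among those still in LTT at that time.

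That would matter little if leaving were unrelated to the outcome. Here both exit reasons bear on the plotted quantity: subjects with few migraines to treat tend to use few doses, and subjects who do not improve may leave for lack of efficacy. The mean for each month is therefore taken over a different and selected group. A reader of a 12-month curve will naturally see durability or waning of benefit, and the label would tell that reader that the curve holds whatever happened to treatment.

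**Working it through.** **1. Which data after discontinuation can enter.** SAP 7.1 sets the end of study drug at the last spray. It sets the end of LTT at the later of the last diary entry and the last visit through Week 52/early termination, leaving out the follow-up visit. So diary days and early-termination questionnaires between the last spray and EOT are used. Beyond EOT nothing is scheduled. The label has some content, but only over that interval.

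**2. Which summaries keep early leavers.**

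| Result | Early leavers included? |
|---|---|
| Migraine days by month (6.4.6.1) | Only in months with at least 14 diary days |
| MSQ, MIDAS, CGI-c by visit (6.5) | Only where they have a value in that visit's window |
| Migraine days, overall LTT (6.4.6.1) | Yes, over each subject's own data days |
| MSQ, MIDAS, CGI-c, PoM, SM at end of study (6.5) | Yes, last post-baseline value |

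**3. Can exit alone move the monthly mean?** The plan gives no figure on this point, so the check is a simulation. From the documents come the 28-day months, 13 months of treatment, the maximum of 8 doses per month, and exit once the mean over 3 consecutive months is below 2 doses. Migraine-day rates, the share of migraine days dosed, the spread of response and the lack-of-efficacy exit rate are assumptions. Each subject's response is constant over time, so any drift is an artefact of exit. Subjects exiting for no use by Week 8 are never in the safety or migraine set, so only the 3-month rule acts, from about Month 4.

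*Model A.* 200,000 subjects; observation-phase (OP) rate gamma with shape 5 and mean 6; 65% of migraine days dosed; individual rate ratio lognormal with median 0.85 and log-SD s. The true mean change is 6 x (0.85 x exp(s²/2) - 1):
- s = 0: 6 x (0.85 - 1) = -0.90
- s = 0.3: 6 x (0.889 - 1) = -0.67
- s = 0.5: 6 x (0.963 - 1) = -0.22

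| Model A scenario | Observed mean change |
|---|---|
| s = 0.3, low-use exit only | -0.66 (Month 3), -0.46 (Month 6), -0.26 (Month 12); 51% remain at Month 12 |
| s = 0.5, low-use exit only | -0.22, +0.63, +1.20 at the same months |
| s = 0, low-use exit only | -0.91 (Month 1) to -1.16 (Month 13) |
| s = 0.3, rule applied to 25% of triggers | -0.67 to -0.46 |
| s = 0.3, 90% of migraine days dosed | -0.66 to -0.46 |
| s = 0.3, plus 5% per month exit of non-improvers | -0.68 to -0.70 |
| s = 0.3, plus 10% per month exit of non-improvers | -0.67 to -1.07 |

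At s = 0 the drift reverses: with a common proportional effect, those who remain have higher rates and hence larger absolute reductions.

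*Model B.* About 60,000 subjects per scenario; entry limited to 2 to 14 OP migraine days (a proxy for the entry criteria); mean rate 6 and 70% of migraine days dosed unless stated. Lack-of-efficacy exit is a monthly chance among subjects whose 3-month mean exceeds their OP count.

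| Model B scenario | Full cohort | Observed, Month 1 to 13 | Drift |
|---|---|---|---|
| Identical response, no effect | about -0.1 | -0.12 to +0.02 | +0.14 |
| Same, mean rate 4 | about -0.32 | -0.32 to -0.08 | +0.24 |
| Same, mean rate 8 | about +0.14 | +0.14 to +0.18 | +0.04 |
| Response SD 0.3, no mean effect | about -0.09 | -0.09 to +0.52 | +0.61 |
| Response SD 0.3, 20% mean reduction | about -1.30 | -1.29 to -0.48 | +0.81 |
| Same, dosing share varying between subjects | about -1.29 | -1.28 to -0.52 | +0.76 |
| Previous row, plus 5% lack-of-efficacy exit | about -1.30 | -1.31 to -1.02 | +0.29 |
| Same, plus 15% lack-of-efficacy exit | about -1.28 | -1.28 to -1.84 | -0.56 |
| Same, 15% lack-of-efficacy exit only | about -1.30 | -1.29 to -2.32 | -1.03 |
| Same, neither exit | about -1.31 | -1.31 to -1.31 | 0.00 |

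**4. The other summaries.** In the 20%-reduction scenarios of Model B, the overall-LTT mean lies between -1.25 and -1.42, against a full-cohort value of about -1.30. In Model A at s = 0.3 with low-use exit, overall LTT is -0.80: an error of 0.14 against a true value of about -0.66, where the Month 12 mean errs by 0.40. Subjects staying to Month 13 in that scenario lie between -0.08 and -0.22 at the months checked: nearly flat, but not at the full-cohort level.

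**The case against.** The case for leaving the plan alone has real force.

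- **Using all observed values is a data-inclusion rule, and the SAP follows it.** This stands in part, because data between the last spray and EOT do enter. A reader might infer that the label is wholly empty; SAP 7.1 does not support that. But a rule about using what exists does not supply outcomes that were never scheduled.
- **Not every mean drops the early leavers.** This stands. Overall-LTT and end-of-study results keep them, and all four migraine-day scatter plots use overall LTT.
- **A reader might infer that forced exit of low users will produce a false fading of benefit.** The documents do not support that. The drift is small or reversed if subjects respond alike, and lack-of-efficacy exit opposes it. Low study-drug use is also not the same as few migraines, since standard-of-care medication is allowed (Protocol 5.5). Perfect enforcement is a worst case: Protocol 6.6 says must and Protocol 7.4 says will, while 4.3.4 and 7.2.2 use may for non-compliance or non-use.
- **No size is known for MSQ, MIDAS or CGI-c.** This stands; only migraine days were simulated.
- **Attrition is already visible.** Kaplan-Meier tables of time in LTT and reasons for exit are planned, and n per time point may be covered by the Core SAP, which is not among the documents. These show how many leave, but not how leaving alters the curve.

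**Conclusion.** The point holds for the label and for the by-month and by-visit results. Treatment policy is not what those results estimate; they describe subjects in LTT up to EOT. A trend in them can come purely from who remains.

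Its direction and size cannot be fixed from the documents. Under the assumptions above, with low-use exit alone, the apparent waning over Months 1 to 13 in Model B is about 0.04 to 0.24 day per month if subjects respond alike and 0.6 to 0.8 if response varies with SD 0.3. Adding lack-of-efficacy exit can cancel or reverse it. This uncertainty means that a reader cannot mentally correct the curve.

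The reach is limited. The endpoints are exploratory, the study has one arm and no hypothesis test, and overall-LTT and end-of-study summaries are less affected. A reader might infer a threat to the safety conclusions, but the primary safety endpoint does not use these data or this strategy.

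**What to change.** 1. In SAP 3.2 and Table 2, describe migraine days, MSQ, MIDAS, CGI-c, PoM and SM as observed-case while in the LTT period, through EOT. Do not substitute the SAP's while-on-treatment strategy unless data are also cut at drug discontinuation, because 3.2 defines that strategy as values before discontinuation.
2. In SAP 6.4.6.1, 6.5.1 and 6.5.4, repeat the by-month and by-visit change tables, and the longitudinal plots, for subjects with at least 51 weeks in LTT. Show n at each time point. Read any time trend alongside the overall-LTT and end-of-study results already planned.
3. Reconcile the protocol wording in 6.6, 7.4, 4.3.4 and 7.2.2 on whether low use or non-use must, will or may lead to discontinuation. No clinical rule is proposed here.

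The cost is SAP wording and a few repeated tables and plots; no new data are needed. The cohort with at least 51 weeks is itself selected, so it shows the trend within subjects who stayed and not the level for all treated subjects. The tables should say so.
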